13.2 STUDY POPULATION

12.2.1 SAMPLE SIZE CALCULATION

A sample of 15-20 participants was chosen according to historical data on tear assessment in this group of participants.

12.2.2 NUMBER OF PARTICIPANTS

Recruitment: Up to 20 participants will be enrolled. Participants who are patients of the University of Waterloo Contact Lens Clinic (UW-CLC) will be invited to participate in this study by their attending doctor. With the patient's permission, the investigators will initiate recruitment according to the in-person script approved by the Office of Research Ethics (Appendix 1). The investigators will discuss the project where any questions regarding the study procedures and any risks associated with the study can be answered. Eligibility will be determined using the inclusion and exclusion criteria. Informed consent will be obtained for all participants prior to their enrollment in the study (Appendix 2).

INCLUSION CRITERIA

A person is eligible for inclusion in the study if he/she:

- Had been diagnosed with keratoconus in at least one eye.

- Is at least 18 years of age and has full legal capacity to volunteer.
- Has read and understood the information consent letter.
- Is willing and able to follow instructions and maintain the appointment schedule.

EXCLUSION CRITERIA

A person will be excluded from the study if he/she:

- Is using any topical medications that will affect ocular health.
- Has any ocular pathology or severe insufficiency of lacrimal secretion (severe dry eyes) that would affect the wearing of contact lenses.
- Has persistent, clinically significant corneal or conjunctival staining using sodium fluorescein dye.
- Has any clinically significant lid or conjunctival abnormalities and active neovascularization.
- Is aphakic.
- Has undergone any corneal surgery.
- Is participating in any other type of eye related clinical or research study.
- Has any known allergies or sensitivity to the diagnostic pharmaceuticals or products, such as fluorescein, used in this study.

13.3 STUDY MATERIALS

12.3.1 VISANTE OCT

The Visante OCT Optical Coherence Tomographer, a standard optometric class II medical device, commercially available in Canada (Health Canada licence #69113), will be used to measure the shape of the eye for contact lens fitting.

12.3.2 PENTACAM

The Oculus Pentacam®, a standard optometric class II medical device, commercially available in Canada (Health Canada licence #69466) will be used for the measure the corneal curvature.

12.3.3 KERATOGRAPH 4

The Oculus Keratograph® 4, a standard optometric class II medical device, commercially available in Canada (Health Canada licence #90001) will be used for the limbal and bulbar redness evaluation and pre-lens non-invasive tear break-up time (NITBUT) measurements.

12.3.4 SEMI-SCLERAL LENSES

The lenses used in this study are approved by Health Canada, with Health Canada license # 29758, and are commercially available. All lenses will be worn during the day only. Lenses will be fitted according to manufacturer's recommended guidelines and participants will proceed in the study only if a suitable fit with the lenses can be obtained. Appendices 9 (Package insert for Boston XO) and 10 (Custom Stable Fitting Guide) are included.

12.3.5 TEAR FILM ANALYSIS

Tear film analysis is performed using antigen capture enzyme linked immunosorbent assay (ELISA). (5) After collection, the tear samples are stored at -80°C until analysis. Preparation of the samples includes dilution with phosphate buffered saline (PBS) containing 1% (w/v) bovine serum albumin and incubation with specific antigen. The tears are assayed for specific proteinase and cytokines using commercially available ELISA kits. Preparation and analysis of samples are as per instructions supplied by manufacturers.

13.4 SCHEDULED AND UNSCHEDULED VISITS

This study has a total of 6 study visits, including the screening visit (see Table 1).

12.4.1 SCREENING

The investigator will determine participant eligibility by reviewing the inclusion and exclusion criteria. Ineligible participants will be advised they do not meet the criteria for the study.

12.4.2 STUDY VISITS

This study will involve 6 visits over 5 study days. The total time commitment for all study visits is approximately 6 hours. The total study visit time commitment may be different for each participant, as the needed visit time will depend on how easily the lenses can be fitted.

The first visit will involve screening of the participants and baseline measurements. The investigator will determine the eligibility of the participant using the inclusion/ exclusion criteria. Ineligible participants will be discontinued from the study. The investigator will also perform baseline tear collection.

At the lens fitting appointment, the participants will be fitted with the scleral contact lenses based on the baseline measurement obtained at the screening appointment. Participants will be instructed on insertion, removal, and proper handling of the lenses.

At each of the lens delivery appointments, the researcher will deliver the study lenses. Measurements, including bulbar hyperemia and pre-lens NITBUT, will be obtained while the participants are wearing the lenses.

After the participant has worn the lenses during the day for two weeks, the participant will return for a follow up visit. At each of the follow up appointments, the lens fit and measurements, including bulbar hyperemia and pre-lens NITBUT, will be repeated while the participants are wearing the lenses. Tear samples will be collected from the study lenses after lens removal.

A wash-out period of minimum of 72 hours is required between the first follow up visit and the second lens delivery visit.

Table 1 provides a summary of the study visits.

Table 1: Summary of visits

Visit code	Visits	Time
0-0	Screening and baseline measurements	1hr±½ hr
1-1	Lens fitting	1hr±½ hr
2-1	Lens Delivery visit - Lens 1	1hr±½ hr
2-2	Follow-up visit - Lens 1	1hr±½ hr
3-1	Lens Delivery visit - Lens 2	1hr±½ hr
3-2	Follow-up visit - Lens 2	1hr±½ hr

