14 PURPOSE AND HYPOTHESIS

The purpose of this study is to investigate changes in the level of inflammatory mediators in the tear film of scleral contact lenses wearers. The hypothesis is that scleral contact lens wear is associated with inflammation in the tear film. Furthermore, the level of proteases and cytokines will be altered in samples collected post scleral lens wear compared to those collected pre-lens wear. Additionally, the amount of alteration will correlate to the fitting characteristics in the limbal zone of the scleral lenses.

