13.5 STUDY PROCEDURES

12.5.1 SCREENING, BASELINE AND EXPERIMENTAL MEASUREMENTS

Screening & Baseline procedure: Participants will present to the screening visit. Their corneal sagittal depth which will be measured with the Visante OCT, auto-refraction and associated visual acuity measurements and corneal topography carried out and biomicroscopy performed, along with hyperemia imaging and pre-lens non-invasive tear break up time. Eligibility will be confirmed and a baseline biomicroscopy assessment will be performed. (Visit 0-0)

Bulbar and Limbal Redness assessment: The eyes of the participants will be imaged using the Keratograph® 4. Participants will be asked to be seated at the Keratograph 4 instrument and will be asked to blink 2-3 times and hold their eye open for a few seconds until the instrument software takes a picture of the eye. This image will be repeated three times.

Flush tear collection method: This procedure entails the instillation of a small amount non-preserved saline, 60 μ L, into the inferior palpebral fold. After which, the fluid can be collected with a micro-capillary tube. (9,10) All samples are collected by the researcher. (Visit 0-0)

Fitting of the semi-scleral lenses: Participants will be fitted each of the two sets of semi-scleral lenses of varying sagittal depth at the limbal zones. Fittings will be done using the corneal sagittal depth which was measured at the screening/baseline visit with the Visante OCT. The lenses will be made of the same gas permeable lens material Boston XO. The lens fit will be evaluated; over-refraction and visual acuity determined. Participants will be instructed on insertion, removal, and proper handling of lenses. (Visits 1-1)

Video Imaging procedure with test lenses: The lens fitting will be imaged using a video-slit lamp and the Visante OCT after the lens delivery appointment (Visits 2-1 & 3-1) and at the follow up appointment. (Visits 2-2 & 3-2)

Pre-lens Non-invasive tear break up time (NITBUT) with test lenses: Pre-lens NIBUT will be measured with the study lens after lens delivery (Visits 2-1 & 3-1) as well as at the follow up visits (Visits 2-2 & 3-2). Participants will be asked to be seated at the Keratograph 4 instrument and will be asked to blink 2-3 times and hold their eye open for a few seconds until the instrument software takes a measurement of the NITBUT. This measurement will be repeated three times.

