Subjective ocular symptom assessment: At the follow up appointment, participants will be asked to rate their ocular comfort, dryness, burning and vision with the contact lenses (Appendix 5). (Visits 2-2 & 3-2)

Table 2 lists a summary of procedures to be conducted at scheduled visits.

Table 2: Summary of procedures to be conducted at scheduled visits

Visit	Procedure	Instrument/ application	Form (Appendix #)
Screening & Baseline visit (0-0)	Informed Consent	-	ICL (2)
	Demographics & History, incl. health, meds, contact lens details	-	Screen/Fitting and Study Visit Form for GP Lenses (3)
	Baseline Tear Collection	-	Biomicroscopy Form (4)
	Sagittal depth measurement	Visante OCT	Screen/Fitting and Study Visit Form for GP Lenses (3)
	Auto-refraction/topography	Auto-refractor/Pentacam	Screen/Fitting and Study Visit Form for GP Lenses (3)
	Vision assessment	Vision charts	Screen/Fitting and Study Visit Form for GP Lenses (3)
	Slit-lamp biomicroscopy (Corneal integrity & staining)	Slit-lamp	Biomicroscopy Form (4)
Lens Fitting (Visits 1-1)	Hyperemia / NITBUT	Keratograph 4	Biomicroscopy Form (4)
	Lens Insertion	-	-
Lens Delivery (Visits 1-1 & 2-1)	Lens examination	Slit lamp	Screen/Fitting and Study Visit Form for GP Lenses (3)
	Auto-refraction/topography	Auto-refractor/Pentacam	Screen/Fitting and Study Visit Form for GP Lenses (3)
	Vision with study lens	Vision charts	Screen/Fitting and Study Visit Form for GP Lenses (3)
	Subjective Best Sphere	Vision charts	Screen/Fitting and Study Visit Form for GP Lenses (3)
	Hyperemia / NITBUT	Keratograph 4	Biomicroscopy Form (4)
	Ocular Symptom Questionnaire	-	Ocular Symptom Questionnaire (5)
Follow-up visit (Visits 1-2 & 2-2)	Lens examination	Slit lamp	Screen/Fitting and Study Visit Form for GP Lenses (3)
	Hyperemia / NITBUT	Keratograph 4	Biomicroscopy Form (4)
	Ocular Symptom Questionnaire	-	Ocular Symptom Questionnaire (5)
	Lens Removal	-	-
	Slit-lamp biomicroscopy (Corneal integrity & staining)	Slit-lamp	Biomicroscopy Form (4)
	Tear Sample Collection from Lens after Lens Removal	-	Biomicroscopy Form (4)

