14 STATISTICAL ANALYSIS AND DATA MANAGEMENT

13.1 STATISTICAL ANALYSIS

All data described above will be analysed at the University of Waterloo from the eye(s) wearing the semi-scleral contact lens(es). Data analysis will be conducted using Statistica 12. Descriptive statistics will be provided on information regarding baseline variables (age, gender, sagittal depth distribution, etc.). Table 3 lists the primary outcome variables and anticipated statistical procedures.

Table 3: Statistical procedures

Variable	Analysis	Statistical test
Parametric (tear clearance, NIBUT, comfort ratings, tear components)	Comparison of lens 1 to lens 2	ANOVA Paired t-test

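### The pre-wear tear sample is a saline flush and both post-wear samples are fluid from the removed lens, so the before-after hypothesis cannot separate scleral wear from collection method

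*Combined protocol and SAP*

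**What the plan says.** The Purpose and Hypothesis section states that "the level of proteases and cytokines will be altered in samples collected post scleral lens wear compared to those collected pre-lens wear", and adds that "the amount of alteration will correlate to the fitting characteristics in the limbal zone of the scleral lenses". Objective 1 likewise calls for tears taken before and after a day's wear.

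Two kinds of sample are described:

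- **Before wear.** Section 12.4.2 places one baseline tear collection at the screening visit. Section 12.5.1 supplies the method: "This procedure entails the instillation of a small amount non-preserved saline", with 60 µL placed in the lower fold and recovered by micro-capillary tube. That paragraph ends "All samples are collected by the researcher. (Visit 0-0", which ties the flush to the screening visit.
- **After wear.** Section 12.4.2 says of the follow-up visits: "Tear samples will be collected from the study lenses after lens removal". Table 2 agrees: "Tear Sample Collection from Lens after Lens Removal".

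No tear sample is listed at the lens delivery visits. Section 12.3.5 covers laboratory handling: "Preparation of the samples includes dilution with phosphate buffered saline (PBS) containing 1% (w/v) bovine serum albumin", followed by commercial ELISA kits. It gives no correction for flush dilution and no bridging between flush and lens fluid. In section 13.1 (Statistical Analysis), Table 3 lists one analysis for tear components: "Comparison of lens 1 to lens 2".

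**The concern.** The first stated hypothesis is that scleral wear is associated with inflammation in the tear film. The natural way to examine it is to set the follow-up samples against the 0-0 sample. Between those two points the participant has worn the lens, but the collection method, the compartment sampled and the dilution have changed as well. A difference could reflect wear, the change of method, or both. A lack of difference could be two effects cancelling.

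The correlation of alteration with limbal fit has the same weakness if alteration is measured from the 0-0 flush, because the method offset may vary between participants and with the volume under the lens. Samples not collected during the study cannot be recovered afterwards.

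**Working it through.** The documents give no figure to reproduce on this point. The check is whether the wear effect can be estimated from the scheduled samples.

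**1. Samples (sections 12.4.2 and 12.5.1, Table 2).** Per eye: a flush at 0-0, lens fluid at 2-2 and lens fluid at 3-2, which makes 3.

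**2. Expected log concentration.** Let *a* be the participant's level, *w* the wear effect, *m* the effect of sampling lens fluid instead of a flush, and *d* the difference between lens designs A and B. Period is left out; it does not change the argument.

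- 0-0 flush: *a*
- Lens fluid, design A: *a + w + m*
- Lens fluid, design B: *a + w + m + d*

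The available contrasts are:

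- A minus flush = *w + m*
- B minus flush = *w + m + d*
- B minus A = *d*

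Only the sum *w + m* can be estimated. The lens contrast *d* is free of both.

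**3. Rank.** With columns intercept, wear, method and lens design, the rows are (1,0,0,0), (1,1,1,0) and (1,1,1,1). The wear and method columns are identical, so the rank is 3 of 4. With participant effects in place of the intercept there are n + 3 columns and the rank is n + 2: 17 of 18 for n = 15, and 22 of 23 for n = 20. With a period column added to the four columns, the rank is 4 of 5. More participants or another model do not change this.

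**4. What a post-removal flush would do.** It adds rows (1,1,0,0) and (1,1,0,1), and the rank becomes 4 of 4. That result leaves visit out of the model. With columns intercept, wear, lens design, visit 2-2, visit 3-2 and method, wear equals the sum of the two visit columns. The rank is 4 of 6 as planned and 5 of 6 with the added flushes. The method alias goes, but wear stays aliased with visit. The 0-0 sample precedes 2-2 by at least 14 days and 3-2 by at least 14 + 3 + 14 = 31 days (two wear periods and the 72-hour washout).

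**5. Direction of the offset (assumption only).** Resident tear volume *V* and the tear share *f* of the lens fluid are not in the documents. With complete mixing, the ratio of lens fluid to flush with no wear effect is *f*(*V* + 60)/*V*. For an assumed *V* = 7 µL:

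- *f* = 5% gives 0.05 × 67/7 = 0.48
- *f* = 20% gives 0.20 × 67/7 = 1.91

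The ratio is 1 when *f* = *V*/(*V* + 60), which is 7.7% for *V* = 5 µL and 33% for *V* = 30 µL. The offset could go either way or be close to nil. The conclusion does not use these values.

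**The case against.** The strongest reply is that Table 3 plans no before-after test, so no planned result is biased. That is correct, and it limits the point. A reader might infer that the planned tear-component analysis is invalid, but the documents do not support that: lens 1 and lens 2 are both sampled from the lens. That comparison may still carry a dilution difference of its own, since the designs differ in limbal sagittal depth, but that is a separate matter. The reply does not rescue the hypothesis, which is left with no test and no pair of samples that could support one.

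A second reply is that fluid under the lens is the compartment of interest and cannot exist before wear. This is fair as a reason to keep the lens-fluid sample. But the hypothesis concerns the tear film and names pre-wear samples as the comparator, so the change of method still matters.

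A third is that the sentence about all samples, placed in the flush paragraph, means a flush was intended throughout. Its visit tag is 0-0, and both section 12.4.2 and Table 2 take the follow-up samples from the lens. If a follow-up flush was intended, the text needs to say so.

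Finally, the protocol describes itself as early feasibility work. That favours a light remedy but does not justify a conclusion about wear that the samples cannot carry.

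**Conclusion.** The concern holds for the before-after hypothesis, for Objective 1, and for the correlation with limbal fit if alteration is measured from the 0-0 flush. Wear and collection method are fully aliased, and no analysis of the scheduled samples can separate them. This rests only on the sampling schedule and on the absence of any stated bridging; it needs no assumption about variance, volume or sample size.

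Two stronger readings are not supported. A reader might infer that the offset is large, or that it would produce a false positive. The documents give neither the standard deviations nor the fluid volumes needed to say so, and the offset could be negligible. A reader might also infer that a follow-up flush would make the wear effect identifiable. It would remove the method alias, but the result would still be an uncontrolled before-after change confounded with visit.

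The wording should be corrected before analysis, because otherwise the first hypothesis rests on a contrast that cannot support it.

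**What to change.** **Needed (wording in section 13.1, Statistical Analysis, before analysis).** State that:

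- flush and lens-fluid concentrations will not be tested against each other;
- any before-after result, or any correlation based on change from the 0-0 flush, is descriptive and not evidence of a wear effect;
- inference on tear components is limited to lens 1 against lens 2, including how that difference relates to the difference in limbal clearance.

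This needs no new data or assays.

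**Optional, if the sponsor wants to keep the before-after hypothesis.** Collect the protocol's own flush after lens removal at 2-2 and 3-2. Preferably also collect it before lens insertion at the delivery visits (2-1 and 3-1), so that the reference is not the screening visit. Keep the lens-fluid sample for the lens comparison, and pre-specify one paired flush-to-flush test on the log scale.

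Samples per eye rise from 3 to 5, or to 7 with delivery flushes. For 20 participants with one eye each, that is 60 to 100 or 140 samples per analyte; for 15 participants, 45 to 75 or 105. ELISA work rises by 2/3 or 4/3, and an ethics and consent amendment would be needed. No visits are added; the time per flush is not given in the documents.

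The limits to state with this option are that the contrast remains confounded with visit and that residual reservoir fluid may carry over into a post-removal flush.

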12.4.3 UNSCHEDULED VISITS

Unscheduled visits will be performed if necessary.

13.5 STUDY PROCEDURES

12.5.1 SCREENING, BASELINE AND EXPERIMENTAL MEASUREMENTS

Screening & Baseline procedure: Participants will present to the screening visit. Their corneal sagittal depth which will be measured with the Visante OCT, auto-refraction and associated visual acuity measurements and corneal topography carried out and biomicroscopy performed, along with hyperemia imaging and pre-lens non-invasive tear break up time. Eligibility will be confirmed and a baseline biomicroscopy assessment will be performed. (Visit 0-0)

Bulbar and Limbal Redness assessment: The eyes of the participants will be imaged using the Keratograph® 4. Participants will be asked to be seated at the Keratograph 4 instrument and will be asked to blink 2-3 times and hold their eye open for a few seconds until the instrument software takes a picture of the eye. This image will be repeated three times.

Flush tear collection method: This procedure entails the instillation of a small amount non-preserved saline, 60 μ L, into the inferior palpebral fold. After which, the fluid can be collected with a micro-capillary tube. (9,10) All samples are collected by the researcher. (Visit 0-0)

Fitting of the semi-scleral lenses: Participants will be fitted each of the two sets of semi-scleral lenses of varying sagittal depth at the limbal zones. Fittings will be done using the corneal sagittal depth which was measured at the screening/baseline visit with the Visante OCT. The lenses will be made of the same gas permeable lens material Boston XO. The lens fit will be evaluated; over-refraction and visual acuity determined. Participants will be instructed on insertion, removal, and proper handling of lenses. (Visits 1-1)

Video Imaging procedure with test lenses: The lens fitting will be imaged using a video-slit lamp and the Visante OCT after the lens delivery appointment (Visits 2-1 & 3-1) and at the follow up appointment. (Visits 2-2 & 3-2)

Pre-lens Non-invasive tear break up time (NITBUT) with test lenses: Pre-lens NIBUT will be measured with the study lens after lens delivery (Visits 2-1 & 3-1) as well as at the follow up visits (Visits 2-2 & 3-2). Participants will be asked to be seated at the Keratograph 4 instrument and will be asked to blink 2-3 times and hold their eye open for a few seconds until the instrument software takes a measurement of the NITBUT. This measurement will be repeated three times.

Subjective ocular symptom assessment: At the follow up appointment, participants will be asked to rate their ocular comfort, dryness, burning and vision with the contact lenses (Appendix 5). (Visits 2-2 & 3-2)

Table 2 lists a summary of procedures to be conducted at scheduled visits.

Table 2: Summary of procedures to be conducted at scheduled visits

Visit	Procedure	Instrument/ application	Form (Appendix #)
Screening & Baseline visit (0-0)	Informed Consent	-	ICL (2)
	Demographics & History, incl. health, meds, contact lens details	-	Screen/Fitting and Study Visit Form for GP Lenses (3)
	Baseline Tear Collection	-	Biomicroscopy Form (4)
	Sagittal depth measurement	Visante OCT	Screen/Fitting and Study Visit Form for GP Lenses (3)
	Auto-refraction/topography	Auto-refractor/Pentacam	Screen/Fitting and Study Visit Form for GP Lenses (3)
	Vision assessment	Vision charts	Screen/Fitting and Study Visit Form for GP Lenses (3)
	Slit-lamp biomicroscopy (Corneal integrity & staining)	Slit-lamp	Biomicroscopy Form (4)
Lens Fitting (Visits 1-1)	Hyperemia / NITBUT	Keratograph 4	Biomicroscopy Form (4)
	Lens Insertion	-	-
Lens Delivery (Visits 1-1 & 2-1)	Lens examination	Slit lamp	Screen/Fitting and Study Visit Form for GP Lenses (3)
	Auto-refraction/topography	Auto-refractor/Pentacam	Screen/Fitting and Study Visit Form for GP Lenses (3)
	Vision with study lens	Vision charts	Screen/Fitting and Study Visit Form for GP Lenses (3)
	Subjective Best Sphere	Vision charts	Screen/Fitting and Study Visit Form for GP Lenses (3)
	Hyperemia / NITBUT	Keratograph 4	Biomicroscopy Form (4)
	Ocular Symptom Questionnaire	-	Ocular Symptom Questionnaire (5)
Follow-up visit (Visits 1-2 & 2-2)	Lens examination	Slit lamp	Screen/Fitting and Study Visit Form for GP Lenses (3)
	Hyperemia / NITBUT	Keratograph 4	Biomicroscopy Form (4)
	Ocular Symptom Questionnaire	-	Ocular Symptom Questionnaire (5)
	Lens Removal	-	-
	Slit-lamp biomicroscopy (Corneal integrity & staining)	Slit-lamp	Biomicroscopy Form (4)
	Tear Sample Collection from Lens after Lens Removal	-	Biomicroscopy Form (4)

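### As listed in Table 2, the follow-up symptom questionnaire comes after the lens-on slit-lamp examination and the Keratograph imaging, and no other text fixes when in the visit comfort is rated

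*Combined protocol and SAP*

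**What the plan says.** Section 12.5.1 places the symptom ratings at the two follow-up visits, 2-2 and 3-2: "participants will be asked to rate their ocular comfort, dryness, burning and vision with the contact lenses (Appendix 5". It does not say at what point in the visit they are taken or who administers the form.

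Table 2 is introduced with "Table 2 lists a summary of procedures to be conducted at scheduled visits". Its follow-up block, labelled "Follow-up visit (Visits 1-2 & 2-2", runs:

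1. lens examination (slit lamp)
2. Hyperemia / NITBUT (Keratograph 4)
3. Ocular Symptom Questionnaire
4. lens removal
5. "Slit-lamp biomicroscopy (Corneal integrity & staining"
6. tear sample from the removed lens

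For redness imaging, 12.5.1 has participants "hold their eye open for a few seconds until the instrument software takes a picture of the eye". For NITBUT they "hold their eye open for a few seconds until the instrument software takes a measurement of the NITBUT". Each is repeated three times.

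Table 3 in 13.1 Statistical Analysis, described there as listing the primary outcome variables, gives "Parametric (tear clearance, NIBUT, comfort ratings, tear components", to be compared between lens 1 and lens 2 by ANOVA or paired t-test. Section 12.1.1 describes a crossover in which investigator and participant are both masked to the lens.

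**The concern.** The comfort rating should describe two weeks of wear and, on the day, 6-8 hours with the lens in. If it is taken after a slit-lamp inspection and repeated open-eye imaging, it may also reflect how the eye feels just after those steps. It also follows an inspection of the fit in the participant's presence, so a remark or reaction could reach the participant before the rating. The two lenses differ in sagittal depth at the limbal zone, which is a feature of the fit being inspected.

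What is at stake is the precision of the comfort comparison, one of the variables the plan calls primary, in a study of at most 20 participants. Under some conditions its freedom from bias is at stake as well.

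**Working it through.** No figure in the plan bears on this point, so the check is a reading of the text followed by a short argument about the paired contrast.

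**Step 1. Does anything outside Table 2 fix the order?** Section 12.4.2 says that lens fit, hyperemia and NITBUT are assessed with the lenses on and that tears are collected after removal. It does not mention the questionnaire. Section 12.5.1 names the visit only. Table 2 is therefore the sole source.

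**Step 2. Can Table 2 be read as a running order?** Broadly, yes. Consent is the first screening row, baseline tear collection is listed before the staining examination, and at follow-up the lens-on rows precede lens removal and the lens-off rows follow it. The table is not a complete sequence, however. Section 12.5.1 requires video slit-lamp and Visante OCT imaging at both follow-up visits, and Table 2 has no row for either. More lens-on procedures of unstated timing may therefore precede the rating.

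**Step 3. What precedes the questionnaire as listed?** Two rows of six: the slit-lamp lens examination and Hyperemia/NITBUT. Open-eye captures per eye: 3 redness + 3 NITBUT = 6. If three repeats means three beyond the first, 4 + 4 = 8.

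**Step 4. What does this do to the lens comparison?** Write the rating of participant *i* with lens *k* as

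Y(i,k) = a(i) + L(k) + P(i,k) + e(i,k),

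where P is any effect of the preceding procedures or examiner contact. The paired difference is

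D(i) = [L(1) − L(2)] + [P(i,1) − P(i,2)] + [e(i,1) − e(i,2)].

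- If P(i,1) = P(i,2), the term vanishes. Absolute ratings shift, but the comparison does not.
- If P varies from visit to visit with the same mean under both lenses, independently of e, the mean of D is unaffected and its variance rises by Var[P(i,1) − P(i,2)]. This is added noise.
- If the mean of P differs by lens, D is biased by that difference.
- If the rating precedes the procedures at one follow-up and follows them at the other, P is present in one rating only and cannot cancel. This is noise if the two patterns balance across lenses, and bias if they do not.

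**Step 5. Could the effect differ by lens?** The NITBUT instruction ties the hold to the software taking its measurement. If that means waiting until break-up is registered, hold length follows NITBUT, which Table 3 itself compares between lenses. The text does not settle whether the hold is that or a fixed few seconds.

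**Step 6. Can it be sized?** No. The documents give no SD for comfort and no estimate of P. The sample-size statement (15-20 participants) carries no effect size, alpha or power.

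**The case against.** The strongest reply is that Table 2 is a summary and nothing requires its rows to be followed in order. That lens removal precedes the lens-off steps says nothing about the order among the three lens-on rows, which is the question here. This stands: a reader might infer that the plan mandates rating only after the procedures, and it does not. The plan is still no safer for it, because an unspecified order can change between a participant's two follow-ups, and then even a constant effect fails to cancel.

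Second, the crossover applies the same list to both lenses, so a common effect drops out. This stands, and it limits the likely harm mainly to noise.

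Third, no passage says these steps cause symptoms. The holds last a few seconds, the Introduction describes a fluid reservoir over the cornea, and NITBUT here is measured on the lens surface. This also stands: provocation is plausible but undocumented. The direction of any lens-dependent effect is unclear too, since a long hold over an intact film is not plainly worse than a short one ending in break-up.

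Fourth, Appendix 5 was not available for this review. If the form asks about the whole wearing period, a few minutes of imaging would matter less.

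Fifth, both parties are declared masked, and nobody is named as administering the form. Examiner influence is a possible route, not a documented unmasking.

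**Conclusion.** The point holds as a timing gap with an unfavourable listed order. A subjective rating among the variables called primary has no fixed place in the visit, and the one table that suggests a place puts it after examination and imaging. The expected consequence is mainly extra noise in the paired difference. Bias needs either an effect that differs by lens or an order that varies between visits. Neither can be sized, and the point rests on the assumption that the procedures or examiner contact can affect a rating at all.

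Several stronger readings are not supported:

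- A reader might take the full slit-lamp examination to come first. Only the lens-on inspection does; biomicroscopy with staining is listed after the questionnaire and after lens removal.
- A reader might treat dryness and burning as primary. Table 3 names comfort ratings only.
- A reader might infer a bias against the lens with the longer NITBUT. That depends on how the hold ends and on a direction of effect the documents do not give.
- A reader might want a power loss. With no SD, effect size or planned power, any figure would only restate the assumption put in.

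This is a minor weakness, worth correcting because the correction is free.

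**What to change.** In Table 2, move the Ocular Symptom Questionnaire to the first row of the follow-up block. In section 12.5.1, add a sentence stating that at visits 2-2 and 3-2 it is completed on arrival, with the lenses in place, before any slit-lamp, OCT or Keratograph procedure and before any discussion of the fit.

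The cost is one moved row and one sentence, with no added procedure, visit time or participants.

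The same move should not be made at the delivery visits. A rating taken straight after insertion would capture insertion and settling discomfort.

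Separately, reconcile the text of 12.5.1, which places the questionnaire at follow-up only, with Table 2, which also lists it at lens delivery. Table 2's codes for the delivery and follow-up visits (1-1 and 2-1; 1-2 and 2-2) should be brought into line with Table 1 and 12.5.1 (2-1 and 3-1; 2-2 and 3-2) in the same edit, so that the new sentence points to the right visits.
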